4.1.2. Safety population (SP)

The Safety population will include all subjects who receive at least one dose of the study treatment. All safety analyses will be based on the Safety population. Subjects will be analyzed as treated.

4.2. Covariates and Subgroups

4.2.1. Planned Covariates

Covariates for analysis of key efficacy data will be identified prior to study unblinding

4.2.2. Planned Subgroups

Subgroups for analysis of key efficacy data will be identified prior to study unblinding

4.3 Management of Analysis Data

4.3.1 TLFs Presentation

Líva v1.2 12Feb2020

All tables, listings and figures will be presented in landscape format. SAS version 9.4 will be used for reporting this study and all outputs will be sent to CSI as electronic files in Rich Text Format (RTF) format documents.

4.3.2 Definition of Analysis Timepoints

The following analysis timepoints will be considered for this study:

Screening/ Baseline (-30 to Day 1)

All screening evaluations are to be considered within 30 days prior to the first dose of PTI-125 (Day 1). Baseline is defined as the last non-missing value on or before the first treatment date.

PTI-125 treatment evaluation period (Day 1 to Day 28)

Subjects will come to the clinic for safety assessment on Day 1, Day 7, Day 14 and Day 28, prior to the morning dose administration.

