5.3. EXCLUSION CRITERIA

Patients meeting any of the following criteria will be excluded from the study:

- 1. Exposure to an experimental drug, experimental biologic or experimental medical device within the longer of 5 half-lives or 3 months before screening
- 2. Enrollment in the previous PTI-125 trial
- 3. A medical condition that would interfere with a lumbar puncture
- 4. Residence in a skilled nursing facility and requiring 24 h care.
- 5. Clinically significant laboratory test results

- 6. Clinically significant untreated hypothyroidism (if treated, thyroid-stimulating hormone level and thyroid supplementation dose must be stable for at least 6 months before screening)
- 7. Insufficiently controlled diabetes mellitus
- 8. Renal insufficiency (serum creatinine > ULN)
- 9. Malignant tumor within 3 years before screening (except squamous and basal cell carcinoma or cervical carcinoma in situ or localized prostate cancer or localized stage 1 bladder cancer)
- 10. History of ischemic colitis or ischemic enterocolitis
- 11. Unstable medical condition that is clinically significant in the judgment of the investigator
- 12. Alanine transaminase (ALT) or aspartate transaminase (AST) > ULN or total bilirubin > ULN.
- 13. History of myocardial infarction or unstable angina within 6 months before screening
- 14. History of more than 1 myocardial infarction within 5 years before screening
- 15. Clinically significant cardiac arrhythmia (including atrial fibrillation), cardiomyopathy, or cardiac conduction defect (patients with a pacemaker are acceptable)
- 16. Symptomatic hypotension, or uncontrolled hypertension
- 17. Clinically significant abnormality on screening electrocardiogram (ECG), including but not necessarily limited to a confirmed QTc value ≥ 450 msec for males or ≥ 470 msec for females.
- 18. Stroke within 18 months before screening, or history of a stroke concomitant with onset of dementia
- History of brain tumor or other clinically significant space-occupying lesion on CT or MRI
- 20. Head trauma with clinically significant loss of consciousness within 12 months before screening or concurrent with the onset of dementia
- 21. Onset of dementia secondary to cardiac arrest, surgery with general anesthesia, or resuscitation
- 22. Specific degenerative CNS disease diagnosis other than AD (eg, Huntington's disease, Creutzfeld-Jacob disease, Down's syndrome, Frontotemporal Dementia, Parkinson's disease)
- 23. Wernicke's encephalopathy

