7.2.3. Study Day 1 (Dosing Initiation)

Patients will come to the clinic in the morning. Prior to dosing, the following assessments will be conducted:

- Confirmation of inclusion/exclusion criteria
- Review of concomitant medications
- Vital signs (blood pressure, temperature, pulse and respiratory rate).
- Listen to heart and lungs
- Cambridge Cognition testing; the average of this result and that of the second screening visit will be taken as the baseline value.
- Blood sample collection for clinical laboratory tests
- Blood sample collection for PTI-125Dx and mTOR assessments (8 mL total)
- ECG

Patients will be administered Study Drug at least 1 h before or after a meal. The patient will be discharged 2 h later with their supply of Study Drug.

After dose on Study Day 1, the following assessments will be conducted:

- Vital signs (blood pressure, temperature, pulse and respiratory rate) at approximately 30 min, and 1 and 2 h post-dose.
- Adverse event monitoring

Clinic personnel will monitor the patients for the occurrence of any adverse events until patients are discharged from the clinic. Upon investigator judgment, patients will be discharged from the clinic with their supply of study drug until the next visit. The caregiver will be instructed to administer study drug twice daily at least 1 h before or after a meal. A dose can be up to 4 h late, but if a dose is missed, the next dose should NOT be doubled.

For all follow-up visits, patients will come to the clinic in the morning and will be instructed not to take their morning dose prior to coming to the clinic.

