10.5. SAFETY ANALYSIS

Adverse events reported on case report forms will be mapped to preferred terms and organ systems using the MedDRA mapping system. Vital signs and clinical laboratory results will be descriptively summarized in terms of change from screening values.

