7.2 Vital Signs

The vital signs include blood pressure, temperature, pulse and respiratory rate. For each scheduled visit, summary statistics will be provided (study population size, mean, SD, minimum, median, and maximum) for each vital sign parameter, by treatment level. Summary statistics for change from screening values will also be presented.

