7.4 Laboratory Data

The clinical laboratory assessments include Hematology, biochemistry and Urinalysis. Laboratory data will be converted to International System of Units (SI units), using commonly available conversion factors. Summary statistics will be based on the converted values. The data listings will contain both the original as well as the converted values.

Descriptive statistics (study population size, mean, SD, minimum, median, and maximum) for each laboratory test and their change from screening values will be presented by treatment group for each scheduled visit.

Axiom Fusion eClinical Suite™Configured for the PTI-125-02 StudyPage 20 of 22

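### Vital-sign and laboratory change is taken from screening although pre-dose Day 1 values exist, and the SAP's date-only baseline rule admits post-dose Day 1 vital signs

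*SAP*

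**What the plan says.** Three places name screening as the reference for safety change:

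- Protocol 10.5: "Vital signs and clinical laboratory results will be descriptively summarized in terms of change from screening values".
- SAP 7.2, for vital signs: "Summary statistics for change from screening values will also be presented".
- SAP 7.4, for laboratory tests: "their change from screening values will be presented by treatment group for each scheduled visit".

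SAP 4.3.2 gives a general rule: "Baseline is defined as the last non-missing value on or before the first treatment date". It sits under a timepoint labelled "Screening/ Baseline (-30 to Day 1"), which puts screening and baseline in one window ending on Day 1.

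Protocol 7.2.3 schedules vital signs, a clinical laboratory sample and an ECG on Day 1 before dosing. Protocol 7.3.1 confirms that the Day 1 laboratory tests are pre-dose. Vital signs are then repeated "at approximately 30 min, and 1 and 2 h post-dose". SAP 2.1 also ends them at 2 h, while the design summary in Protocol Section 4 ends them at 4 h.

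The exclusion criteria in Protocol 5.3 include "Alanine transaminase (ALT) or aspartate transaminase (AST) > ULN or total bilirubin > ULN" and, separately, serum creatinine above ULN. Other laboratory tests and blood pressure are screened by clinical judgement, with no numeric limit.

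**The concern.** A safety change score should show what happened after treatment began. Screening values can be up to 30 days old at the first dose, so change from them also includes whatever moved before treatment. For the four tests capped at ULN, part of that movement is predictable: values selected for being low enough tend to be higher when measured again. SAP 7.0 plans no comparison between treatment levels, so the reader sees within-arm change with about 20 patients per arm, and that is the quantity the drift affects.

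The wording of the baseline rule is a second problem, confined to vital signs. A rule based on date alone cannot tell the pre-dose Day 1 reading from those taken after the dose. If such a post-dose reading became the reference, an acute effect on blood pressure or pulse would be removed from the change score in the active arms, while placebo would have none to remove.

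Safety is listed first among the SAP's primary objectives. The parameters also correspond to nonclinical findings in Protocol Section 2: raised bilirubin with liver changes in the 6-month rat study, and raised blood pressure in high-dose female dogs in the 28-day study.

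**Working it through.** The plan states no figure to reproduce here. The check has two parts.

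**1. What each rule selects as reference**

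The rules are applied to the assessment times in Protocol 7.2.1, 7.2.3 and 7.3.1.

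| Parameter | SAP 7.2 and 7.4, read as Screening Visit 1 | SAP 4.3.2 rule, read literally | Latest value before the first dose |
|---|---|---|---|
| Vital signs | Screening Visit 1 | Day 1, 2 h post-dose (4 h if Protocol Section 4 governs) | Day 1 pre-dose |
| Laboratory tests | Screening Visit 1 | Day 1 pre-dose | Day 1 pre-dose |
| ECG | No change score (SAP 7.3) | Day 1 pre-dose | Day 1 pre-dose |

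The date-only rule goes wrong for vital signs alone. For laboratory tests it already selects the pre-dose Day 1 value.

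Protocol 7.2.4 to 7.2.6 list vital signs on Days 7, 14 and 28 after the dose. Let *a* be an acute post-dose effect that recurs at those visits. Change from a pre-dose reference then shows *a*. Change from a post-dose Day 1 reference shows about *a* − *a* = 0. In the placebo arm *a* = 0 either way.

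**2. Size of the drift in the tests capped at ULN**

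Inputs from the documents: entry requires a screening value at or below ULN (Protocol 5.3), and there are 20 patients per arm (Protocol Section 4).

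Inputs assumed, because the documents give none: screening and later values are bivariate normal with equal means and SDs, their correlation *r* is 0.6 to 0.8, and ULN lies *c* = 1.0 to 1.5 SD above the mean of the unselected candidates.

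Given selection at or below *c*, the mean screening value is −φ(*c*)/Φ(*c*) SD and the mean later value is *r* times that. So:

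drift = (1 − *r*) × φ(*c*)/Φ(*c*)

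- *c* = 1.0: φ/Φ = 0.2420/0.8413 = 0.2876
- *c* = 1.5: φ/Φ = 0.1295/0.9332 = 0.1388

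| ULN position | *r* = 0.6 | *r* = 0.7 | *r* = 0.8 |
|---|---|---|---|
| 1.0 SD | 0.115 SD | 0.086 SD | 0.058 SD |
| 1.5 SD | 0.056 SD | 0.042 SD | 0.028 SD |

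Setting ULN instead by an assumed 5% to 20% of candidates above it gives 0.02 to 0.14 SD over the same correlations.

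Change from Day 1 pre-dose to a later visit has drift (*r* for Day 1 − *r* for the visit) × φ(*c*)/Φ(*c*). This is zero if the two correlations are equal. With 0.7 for Day 1 and 0.6 for the later visit, it is 0.1 × 0.2876 = 0.029 SD at *c* = 1.0, against 0.115 SD from screening.

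For scale, the standard error of one arm's mean change, ignoring truncation, is √(2(1 − *r*)/20): √(0.8/20) = 0.20 SD at *r* = 0.6 and √(0.4/20) = 0.14 SD at *r* = 0.8. The drift is smaller than this in every cell.

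**The case against.** The strongest reply is that the plan names screening for safety change, so no post-dose reading is subtracted from anything. This largely stands. A reader might infer from SAP 4.3.2 that the plan adopts a post-dose baseline for its safety tables. The documents do not support that: SAP 7.2, SAP 7.4 and Protocol 10.5 all say screening, and the date-only rule matters only if that word means the merged screening and baseline timepoint. SAP 4.3.2 also places safety assessments before the morning dose, which suggests pre-dose intent. It does not settle the matter, because the protocol's visit sections and SAP 2.1 schedule vital signs after dosing.

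Second, randomisation makes the drift equal across arms in expectation, and placebo shows its size. This stands, and no bias in the drug-placebo contrast should be inferred.

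Third, SAP 7.4 reports laboratory change at each scheduled visit, and Day 1 is one, so its change from screening displays the pre-treatment drift. This stands in part. Mean changes can be differenced by hand if the same patients contribute, but the SD, median and range of change from Day 1 cannot be recovered.

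Fourth, a reader might credit a Day 1 reference with fewer patients crossing ULN, or with a definite gain in precision. Neither is supported. A patient above ULN at a visit is above it whichever reference is used, and a precision gain depends on how far correlation rises over the shorter gap, which the documents do not say.

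**Conclusion.** The point holds within limits. Screening is a weaker reference for safety change than the pre-dose Day 1 values the trial already collects. For ALT, AST, total bilirubin and creatinine it builds an upward drift of about 0.028 to 0.115 SD into within-arm change. That range rests on assumed correlations and ULN positions, and on Day 1 values not being selected themselves: Protocol 7.2.3 asks for eligibility to be confirmed on Day 1 but states no Day 1 laboratory cut. The drift lies within sampling noise at 20 per arm and leaves the between-arm contrast unbiased in expectation.

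The claim of selection does not extend to vital signs, which face no numeric limit, and the post-dose problem does not extend to laboratory tests or ECG. For vital signs the defect is ambiguity. Two readings of screening give different tables, and one of them could hide an acute drug effect. No size can be given for that, because the documents state no acute effect.

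**What to change.** - In SAP 4.3.2, define baseline for safety as the latest available value taken before the date and time of the first dose: Day 1 pre-dose, with screening used only where that is missing.
- Use this baseline for change in SAP 7.2 and 7.4.
- Align Protocol 10.5, or record the departure in the SAP, as its Purpose section provides for.
- Label all Day 1 post-dose vital signs as post-baseline.
- Reconcile the 2 h end of Day 1 vital signs (Protocol 7.2.3, SAP 2.1) with the 4 h in Protocol Section 4. Likewise reconcile the pre-dose timing of safety assessments in SAP 4.3.2 with the post-dose vital signs in Protocol 7.2.3 to 7.2.6.
- Keep screening as a displayed visit in the tables.

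The CSF baseline stays at Screening Visit 2. The cognition baseline, which Protocol 7.2.3 sets as an average of two tests, is a separate matter that this wording should not be taken to settle.

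The cost is SAP wording plus a protocol alignment or a documented deviation. No new data are needed.

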4.3.3 Data Handling Rules for Unscheduled Visit

Unscheduled tests will be included with the time of the nearest regularly scheduled test. If there is a scheduled test and one or more unscheduled tests assigned to the same time point, the most conservative test (i.e., a test with the lowest or highest results) will be used. Repeated tests will be included only if they reflect abnormal (low or high) results and the corresponding original results are normal.

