7.2. EVALUATIONS BY VISIT

Follow-up visits can be scheduled +/- two (2) days from the actual Study Day number. Please notify Sponsor of changes so that the biomarker lab is aware of whole blood sample shipments.

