7.2.8. Unscheduled Visits and Discontinuation due to AEs

For unscheduled visits due to AEs, any assessments conducted will be at the discretion of the investigator and pertinent to the AE. If a decision is made to discontinue the patient from study drug, the Sponsor will be notified immediately. Restarting the patient on study drug will be a mutual decision by the investigator and the Sponsor.

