7.3. LABORATORY ASSESSMENTS

7.3.1. Clinical Laboratory Tests

The following clinical laboratory tests will be performed at screening, Day 1 pre-dose, and at follow-up visits on Day 7, 14, and 28:

• Hematology: white blood cell (WBC) count with differential, red blood cell (RBC) count, hemoglobin, hematocrit, platelet count.

- Serum Chemistry: glucose, sodium, potassium, chloride, bicarbonate, calcium, phosphate, blood urea nitrogen (BUN), total bilirubin, creatinine, cholesterol, triglycerides, albumin, globulin, total protein, uric acid, alkaline phosphatase (ALP), alanine transaminase (ALT), aspartate transaminase (AST), gamma glutamyl transpeptidase (GGT), lactose dehydrogenase (LDH).
- Urinalysis: color, specific gravity, pH, protein, glucose, ketones and occult blood.

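### The unscheduled-test rule has no pre-dose/post-dose boundary and selects extremes, so pre-dose Day 1 lab and ECG summaries can hold on-treatment values and by-visit means can be shifted

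*SAP*

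**What the plan says.** SAP section 4.3.3 contains three rules.

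- Assignment to a visit: "Unscheduled tests will be included with the time of the nearest regularly scheduled test".
- Choice when a scheduled and an unscheduled test fall at the same time point: "the most conservative test (i.e., a test with the lowest or highest results) will be used".
- Repeats: "Repeated tests will be included only if they reflect abnormal (low or high) results and the corresponding original results are normal".

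Protocol section 7.3.1 schedules clinical labs "at screening, Day 1 pre-dose, and at follow-up visits on Day 7, 14, and 28". For Day 1, protocol section 7.2.3 says "Prior to dosing, the following assessments will be conducted", and the list that follows includes labs, ECG and one set of vital signs. Vital signs are then taken again "at approximately 30 min, and 1 and 2 h post-dose". Under protocol section 7.2, "Follow-up visits can be scheduled +/- two (2) days from the actual Study Day number".

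On what prompts extra tests, protocol section 7.2.8 says "For unscheduled visits due to AEs, any assessments conducted will be at the discretion of the investigator".

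SAP sections 7.2 to 7.4 summarise vital signs, ECG and labs by scheduled visit. Vital signs and labs get descriptive statistics and change from screening; ECG gets counts and percentages in four categories.

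**The concern.** The rule goes by distance in days and ignores the first dose. A lab drawn two days into treatment lies closer to Day 1 than to Day 7, so it is filed with results obtained before any drug was given. If it is the more extreme result, it replaces the true pre-dose value. An early on-treatment abnormality then appears in the Day 1 column of the by-visit table and in none of the later ones. It also makes later visits look better against Day 1.

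The selection rule has a separate effect. Choosing the extreme of two results gives a visit mean that no longer estimates the mean at that visit. Direction is left open for parameters where both low and high matter, such as potassium, glucose or white cell count. For ECG categories, lowest or highest has no evident meaning.

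Safety is a primary objective in SAP section 1.1, and section 7.0 makes the safety analysis wholly descriptive. The by-visit tables, together with the adverse-event tables, are therefore the safety result. Early liver tests are an obvious place where this matters: the protocol's introduction reports hepatic findings in the six-month rat study, and section 7.1 sets liver chemistry thresholds.

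**Working it through.** The plan gives no figure for this rule, so there is none to reproduce.

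**Step 1: which days are filed under Day 1.** Let v be the day of the next scheduled test. A test on day d goes to Day 1 when d − 1 < v − d, that is, when d < (1 + v)/2. Equality is a tie, for which the SAP has no rule.

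- Labs, Day 7 visit on its nominal day: (1 + 7)/2 = 4. Days 2 and 3 go to Day 1; Day 4 is a tie.
- Labs, Day 7 visit held on Day 5: (1 + 5)/2 = 3. Day 2 goes to Day 1; Day 3 is a tie.
- Labs, Day 7 visit held on Day 9: (1 + 9)/2 = 5. Days 2 to 4 go to Day 1; Day 5 is a tie.
- ECG by the schedule table (protocol Appendix A, SAP Table 1), where the next ECG is on Day 14: (1 + 14)/2 = 7.5. Days 2 to 7 go to the pre-dose Day 1 ECG.
- ECG by protocol section 4, which lists Days 7, 14 and 28: as for labs, Days 2 and 3, with a tie on Day 4.

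The ECG sources disagree. Protocol section 4 and SAP section 2.1 include a Day 7 ECG; both schedule tables and the Day 7 visit list in protocol section 7.2.4 do not.

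**Step 2: the effect of taking the extreme.** Assume two normally distributed results on one patient at one time point, with the same mean and SD, correlation ρ and no drug effect. The expected upward shift from using the higher is SD × √((1 − ρ)/π). The documents give no ρ, so a range is shown.

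| Assumed ρ | Shift per affected patient (SD) | Arm difference at 30% vs 10% (SD) |
|---|---|---|
| 0 | √(1/π) = 0.564 | 0.20 × 0.564 = 0.113 |
| 0.5 | √(0.5/π) = 0.399 | 0.20 × 0.399 = 0.080 |
| 0.7 | √(0.3/π) = 0.309 | 0.20 × 0.309 = 0.062 |
| 0.9 | √(0.1/π) = 0.178 | 0.20 × 0.178 = 0.036 |

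The last column assumes that 30% of one arm and 10% of another have an extra test at the visit. Those rates are illustrative. With 20 per arm, the standard error of a difference in means is √(2/20) = 0.316 SD, so the arm difference is between 0.036/0.316 = 0.11 and 0.113/0.316 = 0.36 standard errors. With equal testing rates it is 0.

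These figures apply to the rule for tests that share a time point. The repeat rule acts only when the original is normal and the repeat abnormal, and is not sized here.

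**Step 3: the rules side by side.** Suppose the original is abnormal and a second test is worse. The extreme-value rule selects the second test; the repeat rule excludes it, because the original was not normal. The SAP does not say what separates a repeat from an unscheduled test, so two programmers could produce different tables from the same data.

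**The case against.** The case for leaving the rule alone has real substance.

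- **Baseline is safe.** SAP section 4.3.2 fixes baseline by date, on or before first treatment, and lab and vital-sign changes are taken from screening. A reader might infer that on-treatment values contaminate the reference. They do not; the misfiling affects the Day 1 column and its change from screening.
- **Day 1 is not wholly pre-dose.** Day 1 vital signs include readings up to 2 h after dosing, and SAP section 4.3.2 also counts Day 1 in the treatment period. The boundary problem is therefore one of labs and ECG.
- **Signals have another route.** Protocol section 9.1 treats new clinically significant abnormalities as adverse events, and SAP section 7.1 tabulates treatment-emergent events by arm. SAP section 4.3.4 keeps recorded data in listings. It would be wrong to infer that early drug effects vanish.
- **No test is affected.** SAP section 7.0 rules out between-arm tests on safety parameters.
- **The same rule applies to every arm.** A reader might infer from the adverse-event trigger that the arms are distorted unequally. That needs unequal unscheduled testing, and the documents give no rates.
- **The rule is declared conservative.**

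All but the last stand, and they narrow the point. The last does not: extremes are conservative in a worst-value table but biased in a visit mean, and moving an on-treatment abnormality into a pre-dose column is not conservative. The adverse-event route does not cover changes below clinical significance, which the by-visit summaries are there to show.

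**Conclusion.** The point holds as a defect in a stated rule. Read literally, SAP section 4.3.3 places on-treatment labs from Days 2 and 3 in the pre-dose Day 1 summary on nominal days, with the range moving from Day 2 alone to Days 2 to 4 as the Day 7 visit moves within its window. For ECG the range is Days 2 to 7 if the schedule table governs.

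Choosing the higher of two results shifts an affected patient by about 0.18 to 0.56 SD with no drug effect, assuming normal results and correlations of 0.9 to 0. A difference between arms is possible but not shown. Even at an assumed 30% against 10% extra testing it is small, at most 0.36 standard errors. No limit-exceedance table for labs is planned in the SAP text, so no effect on such a proportion is claimed.

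The consequence is confined to descriptive safety summaries. It is still worth correcting, because those summaries serve a primary objective and the correction is cheap.

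**What to change.** Amend SAP section 4.3.3 as follows.

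1. State that no test taken after the first dose may be assigned to a pre-dose time point. The number of on-treatment days mapped to the pre-dose Day 1 labs or ECG then falls to 0.
2. Use scheduled values only for by-visit summaries and changes. The selection shift in those means becomes 0, and ties no longer matter for them.
3. Show unscheduled and repeat results in listings and in a worst post-dose value table by arm, with lowest and highest values shown separately and the worst category for ECG. This keeps the conservative view and settles direction and the conflict between the two selection rules.
4. Reconcile the ECG days in protocol section 4 and SAP section 2.1 with the schedule tables and protocol section 7.2.4.

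The cost is SAP wording and one table. A patient with only an unscheduled result near a visit would count as missing in that by-visit row, but would still appear in the listings and, if the test was post-dose, in the worst-value table.
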